## JHM IRB - eForm A – Protocol

- Use the section headings to write the JHM IRB eForm A, inserting the appropriate material in each. If a section is not applicable, leave heading in and insert N/A.
- When submitting JHM IRB eForm A (new or revised), enter the date submitted to the field at the top of JHM IRB eForm A.

\*\*\*\*\*  
\*\*\*\*\*

### 1. Abstract

- a. Provide no more than a one page research abstract briefly stating the problem, the research hypothesis, and the importance of the research.

Title: Evaluation of a novel absorbable radiopaque hydrogel in patients undergoing image-guided radiotherapy for borderline resectable and locally advanced pancreatic adenocarcinoma

Pancreatic ductal adenocarcinoma is now the third leading cause of cancer-related death, with a devastating 5-year overall survival (OS) rate of nearly 8%, despite having the 12th most common incidence of all malignancies in the United States [1]. One-third of patients will present with borderline resectable or unresectable, locally advanced pancreatic cancer (BR/LAPC) [2-5]. In the cases of LAPC, chemotherapy with or without radiation may be recommended to improve the quality of life by relieving symptoms and extending survival [6-11]. Despite aggressive combined modality therapy, the median survival remains between 9 and 15 months [12,13].

Current guidelines for the management of BR/LAPC patients include single- or multi-agent chemotherapy or chemoradiation (CRT) in sequence with chemotherapy [14]. Results of studies comparing chemotherapy alone to CRT for patients with BR/LAPC are mixed [6,9,12,15]. The importance of local control or delaying local progression on improving morbidity and possibly mortality in patients with pancreatic cancer is supported by autopsy data demonstrating that 30% of patients die of locally destructive disease [16]. It follows that in the cases of LAPC, advanced radiation therapy techniques using dose-escalation with intensity modulated radiotherapy (IMRT) and stereotactic body radiotherapy (SBRT) are potential strategies to improve local control.

A consistent challenge to dose-escalation with IMRT or SBRT is the sensitivity of the surrounding gastrointestinal organs, particularly the small bowel which is directly adjacent to the head of the pancreas (HOP). For BR/LAPC patients treated with CRT, advances in image guidance have provided the opportunity to safely deliver higher biologically effective doses of radiation therapy using IMRT of >70 Gy (57.25 Gy in 25 fractions, BED 70.36 Gy) compared

Date: 3/13/18

Principal Investigator: [name].

Application Number: IRB00151816

to standard fractionation regimens (50.40 Gy in 28 fractions or 50 Gy in 25 fractions, BED 59.47 Gy and 60 Gy, respectively) [17]. Those patients who underwent dose-escalated CRT with BED>70 Gy, did have a superior OS compared to those receiving BED<70 Gy, supporting the utility of dose-escalation in improving long-term outcomes. SBRT involves a short course of radiation therapy, five fractions or less, and has demonstrated higher rates of local control compared to CRT in other disease sites [18]. Early studies evaluating SBRT for pancreatic cancer utilized single fractions of 25 Gy, resulting in local control rates of 100% at 1 year but unacceptably high rates of gastrointestinal toxicity [19-22]. More recently, hypofractionated SBRT (33 Gy total, 6.6 Gy daily fractions) has been evaluated and utilized by our group in an effort to reduce the toxicity of therapy, with results demonstrating nearly 80% rate of freedom from local progression at one year and an acceptable 11% long-term gastrointestinal toxicity [23]. Outcomes with SBRT are thus promising; however, higher local control rates with dose-escalation may be achievable, but current practice is limited due to risks of toxicity.

The goal of this pilot study is to evaluate the success of an endoscopic ultrasound (EUS) guided injection of TraceIT to mark the interface between the pancreas and duodenum in patients with a pathologically confirmed diagnosis of BR/LAPC pancreatic adenocarcinoma for whom a course of SBRT is indicated. TraceIT is already an FDA approved absorbable tissue marker, however, it has not yet been injected into the region between the pancreas and duodenum in humans. As this is the first in-human experience to attempt to use the hydrogel tissue marker to localize this important boundary, a clinical trial is warranted to investigate the success of this procedure. This study will thus set the stage for a planned future investigation using the TraceIT Tissue Marker as an organ spacing material (AGX-17-001-US) by injecting a larger volume of the hydrogel to displace the duodenum away from the pancreas to reduce risk of duodenum toxicity given the increased distance between the target and the duodenum and with the use of imaging localization..

## **2. Objectives (include all primary and secondary objectives)**

### **Primary Objective:**

To evaluate the success of marking the interface between the pancreas and duodenum with TraceIT Tissue Marker via EUS in patients undergoing image-guided radiotherapy for BR/LAPC pancreatic adenocarcinoma.

### **Secondary Objectives:**

- 1) To assess the visibility of TraceIT on daily cone beam CT acquired as standard of care for image-guided radiation therapy.
  
- 2) To examine the hydrogel injection sites for implant location and presence of local inflammatory reactions as a result of TraceIT placement in patients who proceed to surgical resection.

Date: 3/13/18

Principal Investigator: [name].

Application Number: IRB00151816

**3. Background** (briefly describe pre-clinical and clinical data, current experience with procedures, drug or device, and any other relevant information to justify the research)

Pre-clinical: Our preclinical study on human cadavers was done in September 2016. Using three human cadaveric specimens, TraceIT Tissue Marker was injected between the HOP and duodenum via open laparotomy in one case and endoscopic-ultrasound (EUS) guidance in two cases. Cadavers were subsequently imaged using CT and dissected for histologic confirmation of hydrogel placement. Compared to pre-injection scans, post-injection axial CT demonstrated successful injection of the radiopaque hydrogel as a contrast-enhancing region between the HOP and duodenum. After injection, a pancreatic surgeon dissected each cadaveric specimen by performing an en-bloc resection of the pancreas and the duodenum, preserving the injection site for histologic examination. The tissue was serially sectioned to grossly visualize the injection cavity and sections were then formalin-fixed, paraffin embedded (FFPE) and stained with hematoxylin and eosin (H&E) for microscopic examination of gel placement. Microscopic examination of the FFPE sections following H&E staining revealed a complete separation of the full duodenal mucosa from the pancreatic tissue in most regions without injection into the muscularis propria (Rao et al., IJROBP, 2017).

We have also conducted two distinct preclinical studies on swine animals. The first study assessed for toxicities of direct injection of TraceIT into the pancreas or wall of the duodenum. These studies did not reveal any incidence of pancreatitis or evidence of necrosis of the duodenum by these injections simulating “worse-case” mis-injections of TraceIT when targeting this interface between the HOP and duodenum. In a second porcine study, we were able to demonstrate successful placement of TraceIT via EUS in 6 of the 8 swines. Subsequent imaging on diagnostic CT and cone beam CT (CBCT) demonstrated adequate visibility of the injected TraceIT highlighting the potential utility of TraceIT injection to facilitate visualizing this HOP-duodenum interface on daily image guidance with CBCT.

Clinical: TraceIT Tissue Marker has several publications for marking purposes demonstrating its stability in the esophagus [24], bladder [25], and cervix [26]. Given the unique enzymatic and mobile environment in the peripancreatic region, distinct investigation of the injection in the pancreas-duodenum space is necessary.

**4. Study Procedures**

- a. Study design, including the sequence and timing of study procedures (distinguish research procedures from those that are part of routine care).

This is a prospective, single institution, single arm pilot study to evaluate the feasibility of injecting TraceIT Tissue Marker to mark the interface between the pancreas and duodenum. Six patients with pathologically confirmed BR/LAPC pancreatic adenocarcinoma for whom a course of SBRT is indicated will be enrolled.

Date: 3/13/18

Principal Investigator: [name].

Application Number: IRB00151816

Enrolled subjects will be scheduled for TraceIT placement at the time of standard of care fiducial placement using an endoscopic transduodenal approach with material delivered using an EUS-fine needle in accordance with the manufacturer's instructions. Prophylactic antibiotics will be administered prior to fiducial placement in accordance with institutional practices. At the same time that the fiducials are being placed, TraceIT will also be placed by loading the hydrogel into a syringe and injecting it in the space between the pancreas and the duodenum using a similar needle and procedure as is done during the placement of the fiducial. TraceIT injections will be limited to 0.3 mL to 1.0 mL of material per injection site. The fiducial placement and antibiotics administration are as part of the standard of care. The TraceIT placement is a part of the research. There will be no additional radiation exposure to the patient to place TraceIT.

Standard of care CT planning simulation scans will be performed within 10 days post TraceIT hydrogel placement. These scans will be used to generate the RT treatment plan following Johns Hopkins standard of care to deliver up to 33 Gy in 5 fractions using SBRT within 28 days following TraceIT placement.

The procedure will be determined successful if injected TraceIT is identified between the region of the pancreatic tumor and the duodenum on axial cross-sectional planning CT scan.

Per standard of care, subjects will receive SBRT treatments (up to 33 Gy in 5 fractions) with image-guidance using cone beam CT technology for alignment and will be monitored for radiation toxicity. There will be no additional radiation exposure to the patient to evaluate TraceIT. Following completion of SBRT, patients will proceed with routine standard of care follow-up.

If a patient on study undergoes successful surgical resection, the hydrogel injection sites between pancreas and duodenum will be examined for implant location and to identify any local inflammatory reactions.

b. Study duration and number of study visits required of research participants.

The TraceIT injection will be performed during the endoscopic fiducial placement which is the standard of care. Therefore, there will be no additional study visits needed by patients participating in this study.

c. Blinding, including justification for blinding or not blinding the trial, if applicable.

There is no blinding on this trial.

d. Justification of why participants will not receive routine care or will have current therapy stopped.

Patients will receive the standard of care treatment and will not have routine therapy stopped.

e. Justification for inclusion of a placebo or non-treatment group.

Date: 3/13/18

Principal Investigator: [name].

Application Number: IRB00151816

There is no placebo group in this trial.

f. Definition of treatment failure or participant removal criteria.

Patients will not be enrolled if the routine standard-of-care procedure of fiducial placement cannot be performed.

g. Description of what happens to participants receiving therapy when study ends or if a participant's participation in the study ends prematurely.

Patients will continue to receive the standard-of-care for their radiation therapy treatment.

## 1. Inclusion/Exclusion Criteria

### Inclusion criteria:

Subjects must meet all of the following criteria to be eligible for participation in the study:

1. Age  $\geq 18$  years old
2. BR/LAPC disease as defined by the NCCN guidelines (Figure 1) as follows confirmed via CT, EUS or other imaging modality (e.g., PET):

**Figure 1: NCCN guidelines version 2.2017 for pancreatic adenocarcinoma**

| CRITERIA DEFINING RESECTABILITY STATUS  |   |  |
|---|---|--|
| Resectability Status                                | Arterial  | Venous   |
| Resectable  | No arterial tumor contact (celiac axis [CA], superior mesenteric artery [SMA], or common hepatic artery [CHA]).   | No tumor contact with the superior mesenteric vein (SMV) or portal vein (PV) or $\leq 180^\circ$ contact without vein contour irregularity.  |
| Borderline Resectable                   | Pancreatic head/uncinate process: 

• Solid tumor contact with CHA without extension to celiac axis or hepatic artery bifurcation allowing for safe and complete resection and reconstruction.

• Solid tumor contact with the SMA of <math>\leq 180^\circ</math>

• Solid tumor contact with variant arterial anatomy (ex: accessory right hepatic artery, replaced right hepatic artery, replaced CHA, and the origin of replaced or accessory artery) and the presence and degree of tumor contact should be noted if present as it may affect surgical planning.

 Pancreatic body/tail: 

• Solid tumor contact with the CA of <math>\leq 180^\circ</math>

• Solid tumor contact with the CA of <math>>180^\circ</math> without involvement of the aorta and with intact and uninvolved gastroduodenal artery thereby permitting a modified Appleby procedure (some members prefer this criteria to be in the unresectable category).

 | 

• Solid tumor contact with the SMV or PV of <math>>180^\circ</math>, contact of <math>\leq 180^\circ</math> with contour irregularity of the vein or thrombosis of the vein but with suitable vessel proximal and distal to the site of involvement allowing for safe and complete resection and vein reconstruction.

• Solid tumor contact with the inferior vena cava (IVC).

  |
| Unresectable                            | Head/uncinate process: 

• Distant metastasis (including non-regional lymph node metastasis)

• Solid tumor contact with SMA <math>>180^\circ</math>

• Solid tumor contact with the CA <math>>180^\circ</math>

• Solid tumor contact with the first jejunal SMA branch

 Body and tail 

• Solid tumor contact of <math>>180^\circ</math> with the SMA or CA

• Solid tumor contact with the CA and aortic involvement

   | Head/uncinate process: 

• Unreconstructible SMV/PV due to tumor involvement or occlusion (can be due to tumor or bland thrombus)

• Contact with most proximal draining jejunal branch into SMV

 Body and tail 

• Unreconstructible SMV/PV due to tumor involvement or occlusion (can be due to tumor or bland thrombus)

 |

3. SBRT for local therapy of BL/LAPC is indicated and patient has confirmed intent to undergo SBRT at Johns Hopkins.
4. Subjects Screening/Baseline laboratory testing must meet the following laboratory value criteria:
  - a. White blood cell count:  $\geq 3.0 \times 10^9/L$

Date: 3/13/18

Principal Investigator: [name].

Application Number: IRB00151816

- b. Absolute neutrophil count (ANC):  $\geq 1.5 \times 10^9/L$
- c. Platelets:  $\geq 100 \times 10^9/L$
- d. Total bilirubin:  $\leq 2.0$  times upper limit of normal (ULN)
- e. AST and ALT:  $\leq 3.0$  times institutional upper normal limit
- f. estimated GFR  $>50$
- g. INR:  $< 1.5$   
Hemoglobin:  $\geq 8.0 \text{ g/dL}$
- 5. Zubrod Performance Status 0-2
- 6. Subject or authorized representative, has been informed of the nature of the study and has provided written informed consent, approved by the appropriate Institutional Review Board (IRB) of the respective clinical site.

**Exclusion criteria:**

Subjects who meet any of the following criteria are not eligible for participation in the study:

- 1. Previous thoracic radiotherapy
- 2. Any GI abnormality that would interfere with the ability to access the injection site
- 3. Duodenal invasion detected on endoscopic ultrasound which would exclude candidacy for SBRT
- 4. Active gastroduodenal ulcer or watery diarrhea
- 5. Active bleeding disorder or a clinically significant coagulopathy defined as a PTT $>35$ s or INR $>1.4$  or platelet count less than 100,000 per mm^3.
- 6. Active inflammatory or infectious process involving the gastrointestinal tract based on positive diagnosis or suspected diagnosis in the presence of fever $>38^\circ\text{C}$  or WBC $>12,000/\mu\text{L}$ .
- 7. Compromised immune system: WBC $<4000/\mu\text{L}$  or  $>12,000/\mu\text{L}$ .
- 8. History of Chronic Renal Failure.
- 9. Documented history of uncontrolled diabetes (i.e., symptomatic hyperglycemia that cannot be medically managed, fasting blood glucose level above 300 mg/dL, and/or frequent swings between hyperglycemia and hypoglycemia)
- 10. Currently enrolled in another investigational drug or device trial that clinically interferes with this study.
- 11. Unable to comply with the study requirements or follow-up schedule.
- 12. Any condition or comorbidity that the Investigator believes would interfere with the intent of the study or would make participation not in the best interest of the subject.
- 13. Women of child bearing potential or sexually active fertile men with partners who are women of child bearing potential who are unwilling or unable to use an acceptable method to avoid pregnancy for the entire study

**2. Drugs/ Substances/ Devices**

- a. The rationale for choosing the drug and dose or for choosing the device to be used.

TraceIT Tissue Marker consists of an absorbable polyethylene glycol (PEG) hydrogel with covalently bound iodine (~1%). TraceIT Tissue Marker is indicated for use to radiographically mark soft tissue during a surgical procedure or for future surgical

Date: 3/13/18

Principal Investigator: [name].

Application Number: IRB00151816

procedures. TraceIT hydrogel is intended to mark tissue for at least 3 months after injection. TraceIT Tissue Marker is FDA approved for marking anywhere in the body, including the interface between duodenum and pancreas however this has not yet been attempted in clinical practice.

- b. Justification and safety information if FDA approved drugs will be administered for non-FDA approved indications or if doses or routes of administration or participant populations are changed.

N/a

- c. Justification and safety information if non-FDA approved drugs without an IND will be administered.

N/a

### **3. Study Statistics**

- a. Primary outcome variable:

The success of injecting TraceIT using EUS for guidance will be assessed on post-injection simulation CT scan and determined as successful if TraceIT hydrogel is visible between the pancreatic tumor and duodenum on axial CT.

- b. Secondary outcome variables:

- 1) Visibility of TraceIT on daily cone beam CT acquired as standard of care for image-guided radiation therapy, defined as no visibility, poor visibility, or acceptable visibility by radiation oncologist.
- 2) For patients proceeding to surgical resection, the pathologic specimen will be analyzed grossly and on histopathologic specimen sections for TraceIT placement location and inflammation surrounding placement site.

- c. Statistical plan including sample size justification and interim data analysis.

No formal hypothesis or sample size estimation has been established since this is an early feasibility study with an intent to collect information concerning the procedural characteristics and safety for TraceIT administration within the peri-duodenal space. Six (6) subjects should provide sufficient experience to assess the success of the procedure to result in injecting of the hydrogel marker in the desired location.

No interim data analysis is planned

- d. Early stopping rules.

Date: 3/13/18

Principal Investigator: [name].

Application Number: IRB00151816

If TraceIT placement is unsuccessful as defined by the primary variable outcome in all of the first 3 patients, then the study will be terminated early as this would be an indication that revisions to the procedure would be necessary to facilitate success of the procedure.

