### **Potential Risk Associated with the TraceIT Hydrogel Material (RESEARCH)**

|                  |  |
|------------------|--|
| Likely           | 
 
• N/A
 
  |
| Less Likely      | 
 
• Minor bleeding
 
• Pain
 
   |
| Unlikely         | 
 
• Infection of the blood or other organs Clogging nearby blood vessels by the hydrogel material
 
• Inflammation of the pancreas or surrounding organs causing pain or discomfort
 
• Dislodgement of the TraceIT resulting in tracking to another site
 
• Improper placement of TraceIT into neighboring structures (e.g., duodenal wall)
 
• Foreign body reaction to TraceIT
 
• Delay in starting radiation therapy or surgery
 
 |
| Rare but serious | 
 
• Potential to worsen local progression of the cancer due to undiagnosed/microscopic invasion into the duodenum
 
  |

There may be side effects and discomforts that are not yet known.

b. Steps taken to minimize the risks:

The risks associated with EUS procedures and fiducial marker/TraceIT administration will be minimized via selection of experienced investigators who are skilled in EUS/transduodenal fiducial placement procedures. Additionally, participating gastroenterologist has prior experience with placement of the TraceIT hydrogel in human cadavers. Subjects will be selected and enrolled using clearly defined inclusion and exclusion criteria to ensure the best possible treatment outcome. Additionally, subjects will receive full and careful follow-up.

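### Primary success rule: the aim is to mark the pancreas-duodenum interface, but success needs gel only between tumor and duodenum, so gel inside intervening pancreas would count

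*Combined protocol and SAP*

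**What the plan says.** Section 2 (Objectives) gives the primary objective: "To evaluate the success of marking the interface between the pancreas and duodenum with TraceIT Tissue Marker via EUS". Section 4 (Study Procedures, a) describes the research step as loading the gel and "injecting it in the space between the pancreas and the duodenum". In both, the inner boundary is the pancreas.

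Success is defined twice, each time with the tumor as the inner boundary:

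- Study Procedures, a: "The procedure will be determined successful if injected TraceIT is identified between the region of the pancreatic tumor and the duodenum", read on the axial planning CT.
- Study Statistics, a (primary outcome variable): the injection is "determined as successful if TraceIT hydrogel is visible between the pancreatic tumor and duodenum on axial CT".

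Study Statistics, d stops the trial if the first three placements all fail under the primary outcome definition. Study Statistics, c states that there is no formal hypothesis or sample size calculation; six patients are planned.

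The plan also says what it regards as off target. The Background describes a swine study of "direct injection of TraceIT into the pancreas or wall of the duodenum", presented as simulating worst-case "mis-injections of TraceIT when targeting this interface between the HOP and duodenum". The risk table for the hydrogel lists "Improper placement of TraceIT into neighboring structures (e.g., duodenal wall").

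**The concern.** The objective and the scoring rule name different places. The region between tumor and duodenum contains the pancreas-duodenum interface, and also any pancreatic tissue on the duodenal side of the tumor. Neither success rule asks for the gel to lie outside that tissue or scores gel inside it as a failure. A parenchymal injection, which the plan elsewhere calls a mis-injection, can therefore be recorded as a success.

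This yes/no CT reading is the only primary result. The Abstract and the Benefits section both look ahead to spacer work that depends on feasibility shown here, and gel within the pancreas does not show that the interface can be marked. The same definition decides whether the study stops after three patients, so one such patient among the first three would avert a stop if the other two failed.

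**Working it through.** **Step 1: the wording side by side.**

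| Place in the plan | Inner limit | Outer limit |
|---|---|---|
| Primary objective | pancreas | duodenum |
| Injection site (Study Procedures, a) | pancreas | duodenum |
| Success rule (Study Procedures, a) | region of the tumor | duodenum |
| Success rule (Study Statistics, a) | tumor | duodenum |

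The two readings agree where the tumor reaches the duodenal border of the pancreas. They can differ where pancreas lies in between.

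**Step 2: can such patients enroll?** Yes. No inclusion criterion restricts the tumor to the pancreatic head, and the resectability table also covers body and tail disease. Exclusion criterion 3 removes only duodenal invasion that would rule out SBRT.

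**Step 3: is the reading corrected later?** No. Pathologic location is a secondary outcome, exists only for resected patients, and does not feed back into the primary outcome.

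**Step 4: size per patient.** The plan states no figure to reproduce. With n = 6, one reclassified patient moves the result by 1/6 = 16.7 percentage points. Exact (Clopper-Pearson) 95% intervals:

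- 6/6 = 100%: 54.1% to 100% (lower limit 0.025^(1/6) = 0.541)
- 5/6 = 83.3%: 35.9% to 99.6%

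**Step 5: illustration only.** Let q be the true interface success rate and m the share of interface failures scored as success. Both are assumed.

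- Expected recorded successes among six = 6[q + (1 - q)m]
- P(early stop) = P(no recorded success in the first three) = [(1 - q)(1 - m)]^3

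| q | m | Expected successes of 6 | P(early stop) |
|---|---|---|---|
| 0.75 | 0 | 4.50 | 1.6% |
| 0.75 | 0.25 | 4.88 | 0.7% |
| 0.75 | 0.50 | 5.25 | 0.2% |
| 0.50 | 0 | 3.00 | 12.5% |
| 0.50 | 0.25 | 3.75 | 5.3% |
| 0.50 | 0.50 | 4.50 | 1.6% |
| 0.25 | 0 | 1.50 | 42.2% |
| 0.25 | 0.25 | 2.62 | 17.8% |
| 0.25 | 0.50 | 3.75 | 5.3% |

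For example, with q = 0.50 and m = 0.25, P(early stop) = (0.50 × 0.75)^3 = 0.375^3 = 5.3%. Wrongly averted stops cannot exceed (1 - q)^3, which is 1.6%, 12.5% and 42.2% for the three values of q.

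The value 0.75 equals the 6 of 8 swine placements in the Background, but the plan does not say how success was judged there, so it need not be an interface rate. No value of m can be taken from the documents.

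**The case against.** The strongest reply is that the intent is clear. The operator is told to inject between pancreas and duodenum, and Study Statistics, c refers to the peri-duodenal space and to reaching the desired location. Naming the tumor also has a reason: the later spacer work concerns the distance between target and duodenum in the tumor region. I accept that the interface at tumor level is probably what is meant. But the stopping rule points expressly to the primary outcome definition, so the written definition governs, and it does not say this.

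It is also fair that this is a six-patient pilot with no hypothesis or go/no-go threshold, that a missed stop exposes at most three further patients, and that the illustration rests on assumed inputs. Those points limit the harm but do not remove the mismatch.

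Three stronger readings are tempting, and the documents do not support them:

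- *The rule is looser than the group's own cadaver standard.* The Background says that "post-injection axial CT demonstrated successful injection of the radiopaque hydrogel as a contrast-enhancing region between the HOP and duodenum". That reports what CT showed in three specimens and sets no success criterion. No tumor is mentioned in them, and placement was confirmed by histology. The trial rule is also stricter in one respect, since gel at the interface but away from the tumor would not meet it.
- *Gel in the duodenal wall counts as success.* In plain words such gel is in the duodenum, not between tumor and duodenum. The rule is ambiguous here, no more.
- *Early stopping is seriously weakened.* That needs frequent interface failures and a sizeable m together; neither is documented.

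**Conclusion.** The concern holds as a mismatch between the primary objective and the rule that scores it. Gel in pancreatic tissue between tumor and duodenum meets both written definitions of success, and neither eligibility nor pathology closes the gap. The consequence is a possibly misleading feasibility count, not a wrong formal test and not a demonstrated safety problem.

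Its certain size is one sixth of the result per affected patient. The number affected is unknown, and it is zero if every enrolled tumor reaches the duodenal border or every injection lands at the interface. With a true interface rate of 75% the early-stop probability is at most 1.6% whatever the scoring; a material effect on stopping requires a much lower rate. The point should be fixed, because it touches the only primary endpoint and the remedy is cheap.

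**What to change.** In Study Procedures, a and Study Statistics, a, and so in the stopping rule, define success as gel visible between the pancreas and the duodenum, at their interface, at the level of the tumor on the axial planning CT. State that gel seen only within pancreatic parenchyma, or only within the duodenal wall or lumen, is not a success.

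Add an indeterminate category for reads where CT cannot tell the location. Report the success count twice, with indeterminate reads as successes and as failures, and state before the first patient which count the stopping rule uses.

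The cost is revised wording in the two definitions, a short scoring convention and a slightly longer CT read, with no added scans, visits or patients. The success count may come out lower and some of the six reads may be indeterminate, because the documents do not show that planning CT can separate interface, parenchyma and wall for injections of 0.3 to 1.0 mL per site. If it cannot, reporting that openly is more informative than a count that hides it.
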